Current practice patterns vary widely. In our preliminary analyses, we found wide variation in prescribing of different classes of psychotropic medications to patients with schizophrenia in the year prior to initiation of a new antipsychotic medication, providing additional evidence regarding uncertainty of these treatment strategies. Across states, rates varied by 2 to 3 fold. Specifically, the initiation of benzodiazepines varied from 9.2% (Kentucky) to 29.7% (Vermont); antidepressants from 19.8% (Vermont) to 48.3% (Oklahoma); and mood stabilizers from 6.6% (North Dakota) to 18.9% (Texas). Such variation underscores deficiencies in widely accepted clinical evidence concerning these important treatment decisions.

There is no professional consensus on treatments for important subgroups with schizophrenia. Schizophrenia treatment guidelines and algorithms have concluded that there is little evidence to guide selection of pharmacologic strategies for schizophrenia beyond the initial recommendation for antipsychotic monotherapy and then for clozapine for people with treatment-resistant illness.

Although there is limited information on the clinical comparisons we propose to study, recent evidence from a Finnish observational study of psychotropic polypharmacy in schizophrenia, which used methods that are similar to those that we propose, found substantial effect sizes. In that study, for example, there was a significant increase in mortality associated with adjunctive benzodiazepine use compared to antipsychotic monotherapy and adjunctive antidepressant use was associated with markedly reduced risk of suicide.

Despite the widespread use of various combinations of classes of psychotropic medicines in schizophrenia, their comparative safety and effectiveness have not been established. By determining which options are most effective in achieving desired outcomes in specific clinical situations, this project will promote personalized, evidence-based medicine and has the potential to reduce wasteful or harmful medication management approaches. By helping doctors and patients find effective treatments earlier than by simple trial and error, this project has the potential to reduce the potential harms and inconvenience of failed medication trials, adverse effects, and unnecessary hospitalizations.

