### Data source and cohort identification

The data source will be national (45-state) Medicaid Analytic Extracts data (2001-2010). The cohort will consist of adults who are 18 to 64 years old and diagnosed with schizophrenia who initiate a new psychotropic medication after a period of stable antipsychotic treatment. Individuals who are 65 or older because will be excluded because they also have Medicare and receive pharmacy benefits through Medicare Part D.

Schizophrenia will be defined as  $\geq 2$  outpatient claims or  $\geq 1$  inpatient claim for schizophrenia [ICD-9-CM: 295] during 365 days of consecutive Medicaid enrollment immediately prior to the index date. Stable antipsychotic monotherapy will be defined by filled prescriptions for only one second-generation antipsychotic (excluding clozapine), and no other psychotropics, for  $\geq 90$  days immediately preceding the start of the index medication (t0). After the  $\geq 90$  days of stable treatment with a single second-generation antipsychotic, study patients will have had a change in therapy defined as (1) addition of a second antipsychotic or (2) addition of a different psychotropic drug class (antidepressant, mood stabilizer, or benzodiazepine). To ensure the patients are in active treatment there must be an active supply of antipsychotic medication on t0.

The eligibility criteria select a cohort of individuals that are likely to have schizophrenia, have received antipsychotic monotherapy prior to the index date, and are still experiencing problems for which a new psychotropic medication strategy was initiated. A 1-year period of eligibility prior to follow-up initiation ensures sufficient time to collect service use related covariates to characterize cohort members.

Patients with stable clozapine monotherapy will be excluded because clozapine is largely reserved for the most severely ill patients. Patients who implement more than one change in therapy at the index date (e.g., addition of a mood stabilizer and an antidepressant) will also be excluded.

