### Secondary

We will also investigate time to index treatment discontinuation, time to introduction of another psychotropic medication, psychiatric emergency department visits, all-cause hospitalization, and death.

We will investigate adverse effects of medications including incidence of major cardiovascular events and diabetes mellitus.

Outcomes	
Death	Date of death will be defined by the Social Security Death Master File.
Psychiatric Hospitalization	Hospital claims will define inpatient admissions with a first listed mental disorder diagnosis (ICD-9:290-310). High levels of agreement between diagnoses in inpatient medical records and inpatient claims have been reported for several mental disorder groups, including schizophrenia (100.0%), major mood disorders (98.7%), alcohol dependence (97.8%), and drug dependence (96.4%). 
Psychiatric ED Visits	Emergency department claims are a reliable source of diagnostic information in relation to medical records and a valid source of illness severity information.  Emergency department visits in which the first listed diagnosis is a mental disorder (ICD-9-CM: 290-319) will be defined as emergency department mental health visits.
Self-Injurious Behavior	Deliberate self-harm will be defined by an E-code of E950-E958, excluding late effects of deliberate self-harm (E959), on any inpatient, emergency department, or outpatient claim. High positive predictive values have been reported. 
Diabetes Mellitus	One or more claims with a physician diagnosis of diabetes will define diabetes mellitus. Using self-reported diabetes status as the criterion standard, $\geq 1$ physician claim with any diagnosis of diabetes or a diabetes complication (ICD-9 codes: 295.00-2950.93, 357.2, 362.0-362.02, 366.41) has acceptable sensitivity (68.5%) and specificity (96.9%), and (kappa=0.76).  Sensitivity of 90% and specificity of 93% with self-reported diabetes. 
Cardiovascular Events:	Acute myocardial infarction (AMI) (ICD-9-CM: 410) or stroke (430-438, except 435) will be defined by diagnostic codes on inpatient claims of $\geq 3$ days in duration.  With this AMI definition 75% met criteria for definite or probable AMI on independent review of cardiac biomarkers, electrocardiograms, presenting symptoms, and medical history, and an additional 12% had a suspected AMI. 

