## Approach to confounding

Physicians make treatment choices in light of available clinical information and as a result there is a risk of confounding by clinical indication for the treatments under study. Our design minimizes confounding by indication by focusing on diagnostic subgroups. To further reduce confounding, we will control for a broad range of potentially relevant factors from claims histories. These factors will be identified in the 365-day period before drug initiation and used to calculate propensity scores. In addition we will conduct sensitivity analyses to estimate the extent of unmeasured confounding necessary to fully explain our observed findings and we will conduct instrumental variable analyses if a suitable instrument is identified.

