## Follow-up and censoring

Follow-up will begin at the date of new treatment initiation (t0 or index date) and will end after 365 days regardless of changes in pharmacotherapy (intent-to-treat approach). We will also conduct secondary analyses using a 180-day follow-up period and an as-treated specification. In the as-treated approach, follow-up will end at discontinuation of the new treatment ( $>10$  days without drug) or addition of another psychotropic agent (antipsychotic, mood stabilizer, antidepressant, or benzodiazepine). All analyses will be censored at loss of Medicaid (because that is the data source) with one exception—in intent-to-treat mortality analyses, follow-up will not be censored at loss of Medicaid because date of death data comes from the Social Security Master File, not Medicaid.

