#### AP treatment Initiation year

2002

2003

2004

2005

2006

2007

2008

2009

Diagnostic History, past year	ICD-9-CM Codes*
Depression	293.83, 296.2x, 296.3x, 296.9x, 298.0x, 300.4x, 311.xx
Anxiety	293.84, 300.0x, 300.2x, 300.3x, 308.3x, 309.21, 309.81, 313.0x, 313.2x, 313.89
Bipolar	296.xx (not 296.2x or 296.3x or 296.9x)
Substance use disorder	291.xx, 292.xx, 303.xx, 304.xx
Moderate/severe mental retardation	318.xx
HIV	042, 043, 044, 079.53, V08
Neoplasms	140.xx-239.xx (Exclude people with malignant neoplasms 140.xx-205.xx)
Diabetes	250.xx
Obesity	270.xx
Hyperlipidemia	272.0x-272.4x, 272.7x, 272.9x
White blood cell diseases	288.xx, 289.xx (exclude neutrophil d/o 288.00-288.04, 288.09, 288.1x)
Anemia	280.xx-285.xx
Drug-related dyskinesia	333.85
Hypertension	401.xx-405.xx
Ischemic heart disease	410.xx-414.xx
Pulmonary circulation diseases	415.xx-417.xx
Cardiac dysrhythmias	427.xx
Heart failure	428.xx
Cerebrovascular disease	430.xx-438.xx
Acute bronchitis and bronchiolitis	466.xx
Chronic bronchitis	491.xx
Pneumonia	480.xx-486.xx
Emphysema	492.xx
Asthma	493.xx
Appendicitis	540.xx-543.xx
Noninfectious enteritis and colitis	555.xx-558.xx
Diverticula of intestine	562.xx
Intestinal obstruction	560.xx
Chronic liver disease and cirrhosis	571.xx
Acute & chronic pancreatitis	577.0x, 577.1x
Cholelithiasis	574.xx
Acute kidney failure	584.xx
Chronic kidney failure	585.xx

Kidney infections	590.xx
Cellulitis and abscess	681.xx–682.xx
Osteoarthritis and allied disorders	715.xx
Intervertebral disc disorder	722.xx
Fractures, all sites	800.xx–829.xx
Fracture of neck of femur	820.xx
Poisoning by psychotropic medication	969.xx
Poisonings	960.xx–989.xx
Suicide and self-inflicted injury	E950-959
Intracranial injury	815.xx-854.xx
Severe cardiovascular diseases	401.0x-404.9x, 410.xx-416.xx, 425.xx-437.xx, 440.xx-447.xx
Schizophreniform	295.4x
Schizoaffective	295.7x

---

\* x indicates inclusion of any 5th digit if available for a diagnosis code.

xx indicates inclusion of any 4th and 5th digits if available for a diagnosis code.

Medication history, past year	Drug class
Psychotropic medication	
Antidepressants	SSRI/SNRI/mirtazapine, TCA and heterocyclic compounds, MAOI, trazodone-related antidepressants, bupropion
Mood Stabilizer	lithium, primary anticonvulsant, secondary anticonvulsant
ADHD medication	psychostimulants, alpha-agonists
Anxiolytic/hypnotics	benzodiazepines, GABA agonists, other newer or older anxiolytic/hypnotic

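### Self-harm is counted from any E950-E958 claim with no clean period, so a follow-up claim for an act before t0 can count as a new event

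*Combined protocol and SAP*

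**What the plan says.** The outcome table under Outcomes of interest, Secondary, defines self-injurious behavior by an external-cause code from E950 to E958, "excluding late effects of deliberate self-harm (E959), on any inpatient, emergency department, or outpatient claim". On validity it adds only "High positive predictive values have been reported", with a citation but no figure. The definition sets no limit on setting, diagnosis position or timing. In the same table, myocardial infarction and stroke need an inpatient claim of at least 3 days, and psychiatric admissions and emergency visits need a first-listed mental disorder diagnosis.

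On timing, the Follow-up and censoring section says: "Follow-up will begin at the date of new treatment initiation (t0 or index date) and will end after 365 days". No lag is described.

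The look-back year serves covariates. Data source and cohort identification says "A 1-year period of eligibility prior to follow-up initiation ensures sufficient time to collect service use related covariates to characterize cohort members", and Approach to confounding says "These factors will be identified in the 365-day period before drug initiation and used to calculate propensity scores". Appendix 2 lists "Suicide and self-inflicted injury E950-959" among the past-year diagnoses in the propensity score. Appendix 1 does not list self-harm among the exclusion diagnoses. The Sample size section allows a patient to contribute more than one episode.

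**The concern.** Excluding E959 shows that the outcome is meant to capture new acts and not the aftermath of old ones. That exclusion works only when the aftermath is coded as a late effect. An aftercare visit in the weeks after t0 can carry the code of the act itself, and it is then indistinguishable from a new act under the new drug. A hospital stay or transfer that spans t0 raises the same problem. So does a second episode in a patient who self-harmed during the first.

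False events that are equally common in both groups pull a ratio toward 1. If recent acts are more common in one drug class, they also push the comparison against that class. Readers are likely to look at this outcome by class, because the Goal section cites earlier work in which "adjunctive antidepressant use was associated with markedly reduced risk of suicide".

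**Working it through.** **Reading the definition.** Four elements bear on the question.

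1. Outcome table: E950 to E958 in any setting counts; only E959 is removed.
2. Follow-up and censoring: counting starts at t0 with no lag.
3. Appendix 1: recent self-harm is not an exclusion.
4. Appendix 2: past-year self-harm is a covariate. It affects the weights, not which claims after t0 are events. It also combines E950 to E958 with E959, so it carries no information on how recent the act was.

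No other section supplies a clean period. A claim after t0 that repeats the code for an act before t0 is therefore an event as written.

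**Size.** The plan gives no rate or power figure for self-harm, so there is nothing to reproduce. All inputs are assumptions:

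- I, true 365-day incidence in the reference group: 1% to 3%
- q, share of patients with self-harm shortly before t0: 0.5% to 2%
- c, chance that such a patient has a follow-up claim after t0 with an E950-E958 code: 10% to 50%

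With f = q × c:

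- observed risk = 1 − (1 − I)(1 − f)
- carry-over share in the reference group = (observed risk − I) / observed risk
- observed ratio when the true ratio is 0.70 and f is equal in both groups = [1 − (1 − 0.7I)(1 − f)] / [1 − (1 − I)(1 − f)]

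Mid case, I = 2%, q = 1%, c = 30%, so f = 0.3%:

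- observed risk = 1 − 0.98 × 0.997 = 2.294%
- carry-over share = 0.294 / 2.294 = 12.8%
- observed ratio = (1 − 0.986 × 0.997) / 0.02294 = 0.016958 / 0.02294 = 0.739

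| Case | I | q | c | Carry-over share | True 0.70 seen as | True 1.00 seen as, if q is doubled in one group |
|---|---|---|---|---|---|---|
| Low | 3% | 0.5% | 10% | 1.6% | 0.705 | 1.016 |
| Mid | 2% | 1% | 30% | 12.8% | 0.739 | 1.128 |
| High | 1% | 2% | 50% | 49.7% | 0.851 | 1.497 |

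The last column divides the observed risk with 2f by the observed risk with f. In the mid case this is (1 − 0.98 × 0.994) / 0.02294 = 0.02588 / 0.02294 = 1.128. The doubling is a what-if; the documents do not say that recent self-harm differs by drug class.

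**The 180-day analysis is not a check.** Suppose about half of the mid-case incidence (1%) falls in the first 180 days and all carry-over does. The share becomes (1 − 0.99 × 0.997 − 0.01) / (1 − 0.99 × 0.997) = 0.00297 / 0.01297 = 22.9%, against 12.8% over 365 days.

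**The case against.** The strongest reply is that the problem is possible but not shown. The documents do not say how often aftercare visits repeat E950 to E958, and they cite high predictive values for this kind of claim. At the low end of the assumed ranges, 0.70 becomes 0.705, which is negligible. This stands as a limit on size. It does not answer the point, because a high predictive value without detail does not say whether a claim marks a new act or later care for an old one.

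A reader might also infer that self-harm often prompts the drug change, so that acts cluster just before t0 and bias the comparison between classes. The documents do not support this. The Subgroups section ties the reason for the change to schizophrenia, mood and anxiety diagnoses, and no section mentions self-harm as a trigger.

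Baseline control also goes beyond one variable. Appendix 2 includes psychotropic poisoning, all poisonings, mental health emergency service and graded psychiatric admissions, and the depressive, manic and anxiety subgroups rest on diagnoses within 30 days of t0. These make a large between-class bias less likely. They do not remove false events, and past-year variables do not ensure balance on acts in the last weeks.

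Finally, self-harm is missing from the narrative lists of secondary and adverse outcomes and has no power calculation. That lowers the priority, and the severity below reflects it.

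**Conclusion.** The definition as written can count a follow-up claim for an act before t0 as a new event, and nothing else in the plan prevents it. How often it would do so is unknown. On the assumed inputs, carry-over is about 2% to 50% of counted reference-group events, with a mid case of 13%. With balanced groups the consequence is attenuation: a true 0.70 is seen as 0.705 to 0.851.

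Two stronger readings are not supported: that a large share of counted events will in fact be false, and that the comparison between drug classes is biased. The first depends on coding frequencies that the documents do not give. The second needs an imbalance in recent self-harm that they do not show.

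The point affects one secondary safety outcome and leaves the primary outcome untouched. Severity: minor.

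**What to change.** In the self-harm row of the outcome table:

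- Count an inpatient or emergency claim only when the admission or visit begins after t0. A stay that began before t0 and continues by transfer is not new.
- Count an outpatient E950-E958 claim only if no self-harm act was recorded in the preceding 60 days, including days before t0. Anchor the window to the date on which that act is earliest recorded. Later outpatient claims must not reset it, or true repeats could be suppressed well beyond day 60.

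The 60 days is a working choice. Report sensitivity analyses with other windows, for example 30 and 90 days, and with inpatient and emergency claims only.

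Add self-harm in the 60 days before t0 as a baseline covariate where counts allow. In the smallest cell of Table 5 (611 episodes), an assumed 0.5% to 2% gives only about 3 to 12 episodes (611 × 0.005 = 3.1; 611 × 0.02 = 12.2), so it may not be usable there.

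The cost is a few sentences in the outcome table, one covariate and a short program change; the 365-day look-back already exists. The downside is that a few true early repeats seen only in outpatient care are missed.

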Other psychiatric medication	modafinil, oxybate, phendimetrazine, benzphetamine
OB/GYN medication	oral contraceptives, other contraception, medroxyprogesterone
Metabolic and related medication	lipid-lowering drugs, hypothyroid treatment, antithyroid agents, anorexiant
Cardiovascular medication	thiazide diuretic, ACE inhibitor/ARBs, other anti-hypertensives, other cardiovascular drugs
Respiratory/allergy medication	non-sedating antihistamines, other antihistamines, Corticosteroids, other Asthma medications, Smoking cessation
Gastrointestinal medication	histamine 2 receptor antagonists, proton-pump inhibitors, other prescription dyspepsia, Antacids, anti H pylori, phenothiazine antiemetics, Ulcerative colitis treatment
Neurologic/musculoskeletal medication	migraine treatment/prevention, NSAID, includes coxibs, narcotic analgesic, Non-narcotic analgesic (acetaminophen), Cyclobenzaprine, other skeletal muscle relaxants, other rheumatologic
Antibiotics	
Diabetic medication	
Hyperlipidemia medication	
Severe cardiovascular medication	

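### New diabetes is counted from a single claim, on accuracy figures for having diabetes and with no diabetes-free baseline; if one-year incidence is low, false cases could be a large share of the count

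*Combined protocol and SAP*

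**What the plan says.** Under Outcomes of interest, Secondary, the plan will study adverse effects "including incidence of major cardiovascular events and diabetes mellitus". The outcome table then gives the rule: "One or more claims with a physician diagnosis of diabetes will define diabetes mellitus". Its support is a comparison with what patients report ("Using self-reported diabetes status as the criterion standard"), in which the rule "has acceptable sensitivity (68.5%) and specificity (96.9" per cent), with a kappa of 0.76. A second pair of figures follows: "Sensitivity of 90% and specificity of 93% with self-reported diabetes".

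Under Follow-up and censoring, the primary follow-up "will end after 365 days regardless of changes in pharmacotherapy (intent-to-treat approach"); 180-day and as-treated analyses are secondary.

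On diabetes before the index date, Appendix 1 (exclusion diagnoses) does not list diabetes. Appendix 2 has a past-year diabetes diagnosis (250.xx) and, under past-year medication history, "Diabetic medication", both as propensity-score variables. The quantitative analysis under Sensitivity Analyses deals with unmeasured confounders. No analysis of outcome misclassification is described.

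**The concern.** Sensitivity and specificity against self-report describe how well a claim identifies people who have diabetes. The study needs to identify people who develop it within a year, which is a rarer event. A false-positive rate that matters little when many people have the condition can equal or exceed the true event rate when few develop it.

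The two kinds of error do not offset each other. If error is the same in all arms, imperfect sensitivity alone leaves a risk ratio unchanged, while imperfect specificity pulls it toward 1. Diabetes is one of two adverse effects named in the text, and the Background lists it among the questions patients ask. A diluted comparison could be read as evidence that the strategies do not differ in diabetes risk.

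The missing baseline rule adds a second problem. Without it, patients who already have diabetes can meet the outcome definition as soon as one diabetes claim is filed after the index date.

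**Working it through.** **Inputs from the plan.** Sensitivity (Se) 0.685, specificity (Sp) 0.969 and kappa 0.76; second pair Se 0.90 and Sp 0.93 (outcome table). 1,534 distinct patients per group in the depression subgroup (Sample size).

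**Assumed, because the documents give no value.** True one-year incidence I in the reference arm of 1, 2, 3 and 5%; true risk ratio R = 2.0; the same Se and Sp in all arms; the stated specificity applying to new onset in patients free of diabetes at baseline.

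**1. The plan's own figure.** Kappa is the only number in the diabetes row that can be rebuilt from the others. Scanned over all prevalences, Se 0.685 with Sp 0.969 gives its largest kappa at a prevalence of 23.9%:
- observed agreement = 0.685 × 0.239 + 0.969 × 0.761 = 0.9011
- share positive by claims = 0.685 × 0.239 + 0.031 × 0.761 = 0.1873
- chance agreement = 0.1873 × 0.239 + 0.8127 × 0.761 = 0.6632
- kappa = (0.9011 − 0.6632)/(1 − 0.6632) = 0.706

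The printed 0.76 therefore cannot come from the same table as 68.5% and 96.9%. The 90%/93% pair gives 0.74 at 15% prevalence and 0.78 at 20%, so 0.76 could belong to that pair.

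**2. False share and observed risk ratio.**
- Observed risk at true risk p: Se·p + (1 − Sp)(1 − p)
- False share in the reference arm: (1 − Sp)(1 − I) / observed risk at I
- Observed risk ratio: observed risk at R·I / observed risk at I

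At I = 2%, the reference arm has 0.685 × 0.02 + 0.031 × 0.98 = 0.0441 and the other arm 0.685 × 0.04 + 0.031 × 0.96 = 0.0572. The ratio is 1.30 and the false share is 0.0304/0.0441 = 69%.

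| Assumed incidence | False share, 68.5%/96.9% | True 2.0 appears as | False share, 90%/93% | True 2.0 appears as |
|---|---|---|---|---|
| 1% | 82% | 1.17 | 89% | 1.11 |
| 2% | 69% | 1.30 | 79% | 1.19 |
| 3% | 59% | 1.39 | 72% | 1.26 |
| 5% | 46% | 1.51 | 60% | 1.37 |

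**3. Where half are false.** Setting Se·I = (1 − Sp)(1 − I) gives I = (1 − Sp)/(Se + 1 − Sp) = 0.031/0.716 = 4.33%. For the second pair, 0.07/0.97 = 7.2%. Above these values less than half are false; with the first pair it is 34% at 8% incidence and 29% at 10%.

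**4. Which error matters.** At I = 2%, Se 0.50 with perfect specificity gives 0.020/0.010 = 2.0. Perfect sensitivity with Sp 0.969 gives 0.0698/0.0504 = 1.38.

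**5. A lower false-positive rate for new onset.** At I = 2% and Se 0.685, a rate of 1.0% gives 0.0370/0.0235 = 1.57 with 42% false. A rate of 0.5% gives 0.0322/0.0186 = 1.73 with 26% false.

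**6. Unequal error.** At I = 2% and a true ratio of 1.0, Sp 0.969 in one arm and 0.955 in the other gives 0.0578/0.0441 = 1.31.

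**7. Power.** With 1,534 per arm, I = 2%, R = 2.0 and a two-sided 0.05 test of proportions, power is 90% with perfect measurement and 38% with 68.5%/96.9%.

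**The case against.** A reader might infer that the plan's own specificity shows that half or more of the counted diabetes cases will be false. The documents do not support that. They give no incidence, and the statement fails above 4.3%. The 96.9% was measured against self-reported status. In patients with no diabetes claim in the prior year, people who are miscoded repeatedly would already have been removed, and some claims that disagree with self-report may be true diabetes. The rate that applies to new onset could be well below 3.1%. This stands, and step 5 shows how far the size then falls.

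A reader might also infer that the rule must bias toward no difference and give false reassurance. That needs equal error in all arms. The arms are different drug classes, and nothing in the documents shows equal testing or coding. Step 6 shows a false harm arising from a modest difference in specificity.

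A third tempting reading is that the printed code range, 295.00-2950.93, will be programmed as it stands. It begins with the schizophrenia code that defines the cohort, but Appendix 2 uses 250.xx for diabetes, so a misprint is the likelier explanation. It needs reconciling and does not show that the outcome will be built wrongly.

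Finally, a stricter rule is not certain to gain power. In the setting of step 7, an assumed 50%/99.5% rule has 50% power, but 35%/99.5% has 34% and 50%/98.5% has 35%, both below the 38% of the one-claim rule. This also stands. The case for confirmation rests on reducing false cases and on seeing whether results depend on the definition.

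**Conclusion.** The concern holds in conditional form. The plan uses a one-claim rule, validated for having diabetes, to count new diabetes over 365 days. It writes no diabetes-free baseline, no confirmation step and no misclassification analysis. Those gaps are in the text and need no assumption.

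The size does need assumptions. At least half of the reference-arm cases would be false only if incidence is about 4.3% or less and the 96.9% carries over to new onset equally in all arms. Under that equal-error condition a true 2.0 is reduced to between 1.17 and 1.51 over assumed incidence of 1 to 5%. Milder false-positive rates shrink the effect without reversing it. Without equal error, neither the direction nor the size can be stated. Confidence in the magnitude is medium at best, because the accuracy figures do not agree with each other.

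This is a secondary safety outcome; the primary outcome is unaffected. The definition should be changed before the diabetes comparisons are interpreted.

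**What to change.** - Restrict the diabetes analysis to patients with no diabetes claim and no antidiabetic fill in the 365-day baseline. A confirmed rule needs this restriction, because existing treated diabetes would otherwise meet it easily.
- Define incident diabetes as two or more diabetes claims on separate dates, or one claim plus a filled antidiabetic drug, during follow-up. Date the event when the rule is met.
- Report the one-claim rule alongside, in the same diabetes-free cohort.
- Add a quantitative sensitivity analysis over a range of sensitivity and specificity, including unequal error by arm.
- Check 68.5%, 96.9% and kappa 0.76 against their source, and reconcile the printed code range with the 250.xx in Appendix 2.

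**Cost.** Revised outcome wording, antidiabetic fills extracted during follow-up (Appendix 2 lists them only as past-year history) and a re-run on data already held. Fewer true cases will be captured, and power may fall if the stricter rule loses much sensitivity. The 180-day and as-treated analyses leave less time to confirm a case, possibly unevenly by arm, so the two rules should be shown side by side there as well.

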## Analysis plan

**AIM 1 Comparative Effectiveness: Main Effects:** Within five clinically important schizophrenia subgroups, compare the effectiveness and safety of alternative medication strategies beyond antipsychotic monotherapy.

We will construct Cox models to estimate effects of the study treatments. We will first examine unadjusted treatment effects and then will conduct analyses using basic adjustment for demographic factors. Then we will construct Cox models using weighted propensity scores. Follow-up time will be censored at discontinuation or change of second drugs, death, or loss of Medicaid.

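### The AMI/stroke outcome needs a stay of at least 3 days with no exception for early death, so admissions fatal before day 3 are missed as cardiovascular events; the stroke code range should also be limited to acute codes

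*Combined protocol and SAP*

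**What the plan says.** Under Outcomes of interest, Secondary, the plan names two adverse effects: "We will investigate adverse effects of medications including incidence of major cardiovascular events and diabetes mellitus". The outcome table defines the cardiovascular events as AMI (ICD-9-CM 410) "or stroke (430-438, except 435) will be defined by diagnostic codes on inpatient claims of" 3 days or more. No exception is made for a shorter stay that ends in death, and no diagnosis position is stated. In support, the table reports that "With this AMI definition 75% met criteria for definite or probable AMI", with a further 12% suspected.

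On death, the table says "Date of death will be defined by the Social Security Death Master File". The Aim 1 text of the Analysis plan says "Follow-up time will be censored at discontinuation or change of second drugs, death, or loss of Medicaid".

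Other outcomes in the same table carry restrictions that this one lacks. Self-harm is defined "excluding late effects of deliberate self-harm (E959"). For the primary outcome, "Hospital claims will define inpatient admissions with a first listed mental disorder diagnosis". In Appendix 2, codes 430 to 438 form the past-year history covariate for cerebrovascular disease.

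**The concern.** A length-of-stay minimum makes a claims definition more specific, but without an exception for death it also screens out the most severe true events. A patient admitted with AMI or stroke who dies on the first or second day does not meet the definition and is then censored at death. None of the planned sensitivity analyses (180-day follow-up, as-treated, diagnoses from more than one provider, unmeasured confounding) varies this definition.

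The stroke codes raise a related problem. The outcome is meant to measure incidence, yet its range is the plan's own history category with only 435 removed. Appendix 1 does not exclude patients with earlier AMI or stroke, so people with old disease are in the cohort. If the range contains codes for old or late-effect disease, such a code in any position on a stay of 3 days or more would count as a new stroke. That includes psychiatric stays, so a strategy that changes psychiatric admissions could appear to change strokes.

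**Working it through.** The plan gives no event rate, event count or power for AMI/stroke, so there is no stated figure to reproduce. The Sample size section names only hospital admission as the outcome in its worked examples. Every share below is an assumption chosen to show a range.

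**How the event is lost.** The outcome table requires a stay of at least 3 days. Death before day 3 makes the stay too short, and the Aim 1 text ends follow-up at death. The cardiovascular analysis therefore records a censored non-event. The same death is counted in the all-cause death outcome, but the named source is cited for the date only, so nothing marks the death as cardiovascular.

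**Equal loss in both arms.** Let f be the share of events fatal before day 3.
- Observed ratio = true ratio × (1 − f)/(1 − f) = true ratio. There is no bias.
- Take a hazard ratio of 1.5, equal group sizes and two-sided alpha of .05. Events needed for 80% power: 4 × (1.96 + 0.84)² / (ln 1.5)² = 191.
- Power with D events: Φ(√(D/4) × ln 1.5 − 1.96).

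| f | Events kept | Power |
|---|---|---|
| 0% | 191 | 80% |
| 5% | 181 | 78.0% |
| 10% | 172 | 75.7% |
| 20% | 153 | 70.7% |

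**Unequal loss.** With f1 in the compared arm and f0 in the reference arm, observed ratio = true ratio × (1 − f1)/(1 − f0).
- f1 = 20%, f0 = 10%: 0.80/0.90 = 0.89 for a true 1.00, and 1.5 × 0.80/0.90 = 1.33 for a true 1.5.
- f1 = 10%, f0 = 5%: 0.90/0.95 = 0.95 for a true 1.00.

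The arm with more rapidly fatal events looks safer than it is.

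**Stroke codes, if the range does include non-acute disease.** Let q be the share of reference-arm events that are non-acute and unrelated to treatment. Observed ratio = (1 − q) × 1.5 + q.

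| q | Observed ratio for a true 1.5 | Events for 80% power |
|---|---|---|
| 0% | 1.50 | 191 |
| 10% | 1.45 | 228 |
| 30% | 1.35 | 349 |
| 50% | 1.25 | 631 |

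This dilution needs no difference between arms. It does depend on what the codes mean, which the documents do not say.

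**The case against.** The definition is tied to cited validation work, and accepting lower sensitivity for higher specificity is a defensible choice. That stands as far as it goes: the case is for an exception to the stay rule, not for dropping it. However, the quoted 75% and 12% describe AMI claims that met the definition. They say nothing about events that the stay rule misses, and nothing about stroke.

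A reader might infer that these patients vanish from the study, or that the hazard ratio is biased. The documents support neither. The deaths enter the death outcome, and intent-to-treat mortality follow-up continues after loss of Medicaid. Nothing in the plan suggests that early fatality differs by strategy, so 0.89 illustrates a possible bias and does not estimate one.

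A reader might also infer that old strokes are certain to be counted as new. The documents never define 438. The broad label in Appendix 2 gives reason to check the code book but does not settle the matter. Past-year cerebrovascular disease is in the propensity score, which should help to balance old disease between arms, but it does not remove false events recorded on admissions after the index date.

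Finally, a first-listed rule might look like the plan's standard. It is not: self-harm and diabetes have no such rule, and the psychiatric outcomes use it to establish the reason for the visit. As a requirement, it would drop a true AMI or stroke coded second during a psychiatric stay, and would depart from the AMI definition as written.

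**Conclusion.** The concern holds for one secondary safety outcome and does not touch the primary outcome. Followed as written, the plan misses AMI and stroke admissions that are fatal before day 3 as cardiovascular events. With equal losses, the cost is understated event rates and lower power, from 80% to about 78, 76 or 71% at assumed losses of 5, 10 or 20%. Bias in the ratio requires early fatality to differ by arm, which the documents neither show nor rule out. The stroke range is broad enough to need restricting to acute events, but how many non-acute codes it would admit cannot be determined from the documents.

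**What to change.** In the cardiovascular row of the outcome table, count a qualifying AMI or stroke inpatient claim if the stay is at least 3 days **or** the patient died, by the Death Master File date, during the stay or within 3 days of admission. The plan already uses that death date, so no new data source is needed. The downside is small: a few early deaths with a wrong admission code will be counted.

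In the same row, restrict stroke to acute-event codes. Check 430 to 438 against the code book and remove any late-effects code, as is done for self-harm with E959.

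Use first-listed position as a sensitivity analysis only. State as a limitation that fatal events outside hospital cannot be recovered, because no cause-of-death source is named.

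The cost is a short edit to one table row, one added sensitivity analysis and the matching claims coding.
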